### Baseline Conditions

Chronic diseases, current observable conditions, any new clinically relevant findings discovered from the physical examination, ECG, safety labs, and any condition requiring therapy (excluding CD) will be reported on the baseline condition eCRF page.

Patients who have a laboratory test value outside the range specified by the inclusion criteria may have the test repeated to determine eligibility. The result must be available prior to Visit 2 (Day 1).

### Demography

Informed consent date, gender, age, race and ethnic origin will be collected in the eCRF page. Also, the patient's smoking history will also be assessed. Information concerning race/ethnicity will be collected as it has been suggested that there might be race/ethnicity variations in the incidence, phenotypic manifestations and outcome of CD. Note: In some countries, race may not be collected.

### Medical and Surgical History

Information on clinically significant previous and concomitant illnesses, other than CD, or any clinically significant signs or symptoms that are present before informed consent, or pre-existing conditions identified through findings from assessments and examinations done during the screening visits will be recorded as medical and surgical history at screening. For

planned procedures/hospitalisations during the trial, documentation should be completed at the time of the screening.

Regarding the CD, a detailed history of the disease, including date of diagnosis, disease location, behaviour and severity, surgeries, hospitalizations, and extraintestinal manifestations will be collected.

Also, previous and concomitant treatment for CD will be recorded.

#### Physical examination and vital signs

Please refer to [section 5.2.1](#) and [5.2.2](#).

#### Imaging: MRI

MRI will be performed as described in the [Flow Chart B](#).

Decision on eligibility of patients is based on assessment by investigator(s) on site.

MRI will be read by independent assessor(s) who determine the [REDACTED] for efficacy outcome measures purposes, cf. [section 5.1](#).

MRI results to be reviewed PRIOR to surgical procedures at visit 1c.

#### Blood sampling

Blood samples will be taken for safety laboratory, and infection screening according to [Flow Chart B](#).

For women of childbearing potential, a serum pregnancy test will be performed.

For further details, please refer to the lab manual (ISF).

#### Stool sampling

A stool sample will be collected to exclude existence of enteric pathogens. If collection is not possible at Visit 1a, stool sample has to be collected at (or prior to) Visit 1c. For further details, please refer to the lab manual (ISF).

If the time window for Screening Visits 1a and 1b is other than is specified in the Flow Chart, this should be agreed at the discretion of the PI, in alignment with the trial monitor on a case by case basis.

Re-screening will be allowed.

For a detailed description of the trial procedures at Visits 1a and 1b, please refer to the [Flow Chart B](#).

#### 6.2.2.2 Fistula preparation visit 1c and visit 4

The Visit 1c should take place 3 weeks (-21 days + 4 days) *prior* to Visit 2.

The visit 4 should take place 4 weeks (29 days  $\pm$  4 days) *after* visit 2

In- and Exclusion criteria to be checked prior to performing the surgical visit.

[REDACTED]

Biopsies

During the fistula preparation visit 1c, the fistula(s) will be drained and a *seton will be placed*.

Based on the outcome of the Screening Cohort (gene expression analysis by RNAseq), it will be decided whether eligibility criteria have to be amended for Study Cohort.

- If only the tissue from the inner orifice but not the fistula canal allows assessing gene expression changes the eligibility criteria for Study Cohort will be amended to require the availability of an inner orifice biopsy during the baseline FPV.

The following samples will be collected at visit 1c and 4 from all perianal fistulas drained by a seton:

- Biopsy at the inner fistula orifice, *mandatory*
- Curettage of the fistula canal

○ [REDACTED]

- If both tissue sources (inner orifice and fistula canal) allow assessing gene expression changes, the eligibility in study cohort will not need to limit the study population to patients where both tissues are available from the baseline FPV.

The following samples will be collected at visit 1c and 4 from all perianal fistulas drained by a seton:

- Biopsy at the inner fistula orifice, *optional*
- Curettage of the fistula canal

○ [REDACTED]

*Screening Cohort tissue analyses have shown that all tissue sources allow assessing gene expression. However, they have also shown differences in gene expression depending on the tissue location. (inner / outer fistula orifice and curettage). Thus, it has been decided:*

1. Not to change the eligibility criteria: No need to limit the study population to patients where both, tissue from the inner orifice and fistula canal, are available
2. To keep the tissue sampling approach as stated in the screening cohort and described below:

The following samples will be collected at visit 1c and 4 from all perianal fistulas drained by a seton placed at visit 1c:

- Biopsy at the inner fistula orifice
- Curettage of the fistula canal

○ [REDACTED]

○ [REDACTED]

During the fistula preparation visit 4, the *seton will be removed*.

Results from the biopsies at visit 1c and 4 will be used for primary endpoint analysis.

Refer to Section 15 of the ISF for details.

Please refer to [section 4.2.2.2](#) for surgical restrictions.

[REDACTED]

#### Physical examination and vital signs

Please refer to [section 5.2.1](#) and [5.2.2](#).

#### Blood sampling

Blood samples will be collected according to [Flow Chart B](#). For further details, please refer to the lab manual (ISF).

#### Stool sampling

Stool samples will be collected according to [Flow Chart B](#). For further details, please refer to the lab manual (ISF).

For a detailed description of the trial procedures at Visits 1c and 4, please refer to the [Flow Chart B](#).

6.2.2.3 Treatment period(s): Visit 2, Visit 3 and Visit 5 to End of Treatment (EoT) Visit

All procedures from visit 2, visit 3 and visit 5 to End of Treatment (EoT) Visit are displayed in this chapter since all visits have nearly the same structure.

Study related procedures will be performed as specified in the [Flow Chart B](#) and [C](#).

[REDACTED]

[REDACTED]

Imaging: MRI and [REDACTED]

MRI will be performed as described in the [Flow Chart B](#) and [Flow Chart C](#).

Decision on progress of patients is based on assessment by investigator(s) on site.

MRI will be read by independent assessor(s) who determine the [REDACTED] for efficacy outcome measures purposes, cf. [section 5.1](#).

*Visit 6:*

MRI to be performed in a time window of 2 weeks PRIOR to visit 6. MRI result to be available at visit 6 for the evaluation of combined perianal fistula remission.

The treatment decision for period 2 is based on the evaluation of combined perianal fistula remission performed by investigator(s) on site (cf. [chapter 3.1](#) and [5.1](#)).

[REDACTED]

Physical examination and vital signs

Please refer to [section 5.2.1](#) and [5.2.2](#).

Blood sampling

Blood samples will be collected according to [Flow Chart B](#) and [C](#). For further details, please refer to the lab manual (ISF).

Stool sampling

Stool samples will be collected according to [Flow Chart B](#) and [C](#). For further details, please refer to the lab manual (ISF).

Roll-over to open label long-term extension study 1368-0007

All patients of study cohort completing week 24 of the study and having an individual clinical benefit may be offered to enter open label long-term extension study 1368-0007, which offers open label active treatment with subcutaneous BI .

Patient information for trial 1368-0007 (for patients to whom the roll-over trial 1368-0007 will be offered) may be performed during visit 8 since visit 9 is coinciding with the first visit for trial 1368-0007 in most cases.

Unscheduled visits

The patient may be called in for additional unscheduled visits due to safety reason at the discretion of the investigator or the sponsor, unless the patient has withdrawn his/her consent. The patient may also contact the site due to safety reason for an unscheduled visit.

The unscheduled visit may include additional collection of blood samples for safety reasons. The unscheduled visit may also include additional assessments deemed necessary by the investigator such as laboratory samples, ECGs, or other procedures which were missed at a previous visit.

All unscheduled visits should be described (including the reason for the visit) and documented in the medical/source record, and in the eCRF.

#### 6.2.2.4 Follow up period and trial completion

For all patients, termination of trial medication and trial completion must be recorded on the corresponding eCRF.

For patients completing the safety FU period, the EOS visit is scheduled at 16 weeks after the last dose of study drug, ie at week 36 for those discontinuing after completing 24 weeks of treatment.

All patients of study cohort completing week 24 of the study and having an individual clinical benefit may be offered to enter open label long-term extension study 1368-0007, which offers open label active treatment with subcutaneous BI 655130. These patients are not requested to complete the follow up visit (V 10). They will have their last study visit at visit V09, probably co-inciding with the first visit in 1368-0007. For AE and concomitant therapy reporting the end of study participation is defined as the day of first administration of study drug in 1368-0007.

#### Early treatment discontinuation

Patients of study cohort who terminate study drug early should be encouraged to follow all study procedures per the Flow Chart until week 24, but not receive any more study drug at the respective visits. Given the patient's agreement, the patient will undergo the procedures for early treatment discontinuation and follow up as outlined in the [Flow Chart](#) and [Section 6.2.2.3](#).

#### Further treatment after the end of the trial

At the end of the trial, patients will be treated for their CD at the discretion of the investigator, according to local CD guidelines.

#### Trial completion

Trial completion is defined as a patient having reached the EOS visit or day of the first administration of Spesolimab in 1368-0007. EOS visit will be at week 36 (Visit 10) for patients who will not enter subsequent maintenance trial.

Last visit will be at week 24 (Visit 9) for patients rolling-over into subsequent maintenance trial. But individual patient's end of trial is defined as the day of first administration of Spesolimab in 1368-0007.

Regarding instructions for drug administration at missed or delayed visits, please refer to [Section 4.1.4](#).

## 7. STATISTICAL METHODS AND DETERMINATION OF SAMPLE SIZE

This section is only applicable for the Study Cohort. Planned analyses for the Screening Cohort will be defined in the TSAP. These will be separate from the analyses for the Study Cohort and will comprise the analysis of disposition, AEs and [REDACTED].

### 7.1 STATISTICAL DESIGN - MODEL

The trial objectives and endpoints are stated in [section 2](#).

### 7.2 NULL AND ALTERNATIVE HYPOTHESES

It is not planned to test any statistical hypotheses in a confirmatory sense.

The results including confidence intervals and (adjusted) p-values will be discussed and interpreted in the perspective of the exploratory character of the study.

### 7.3 PLANNED ANALYSES

All individual data will be listed.

The statistical analysis of the Screening Cohort will be based on the following analysis sets:

- Enrolled set (ES – Screening Cohort)  
This patient set includes all patients of the Screening Cohort who signed informed consent.  
It will be used for analyses of patient disposition.
- Entered set (ENTS – Screening Cohort)  
The entered set includes all patients of the Study Cohort who entered the trial.

The statistical analysis of the Study Cohort will be based on the following analysis sets:

- Enrolled set (ES – Study Cohort)  
This patient set includes all patients of the Study Cohort who signed informed consent.  
It will be used for analyses of patient disposition.
- Randomised set (RS): The randomised set includes all randomised patients, whether treated or not.  
Since patients in the Screening Cohort will not be randomised, RS only contains patients of the Study Cohort.
- Safety set (SAF): The safety set includes all patients who were randomised and treated with any amount of study drug. The treatment assignment will be determined based on the actual treatment the patient received.  
Since patients in the Screening Cohort will not be randomised, SAF only contains patients of the Study Cohort.
- Full analysis set (FAS)  
The full analysis set includes all patients of the Study Cohort who provided a baseline value and at least one post-baseline value for at least one secondary endpoint or

further efficacy endpoint. Following the intent-to-treat principle, patients will be analysed according to the treatment they were assigned to at randomisation.

- RNA sequencing set (RSS): This patient set includes all patients in the safety set who provide a valid baseline and at least one valid post-baseline observation for at least one gene expression variable of biopsy. This patient set will be used for analyses related to RNA sequencing.

By definition of the safety set, RSS only contains patients of the Study Cohort.

In the TSAP, the FAS definition may be updated, and further analysis data sets may be defined.

The following analyses of this trial protocol, in chronological order, are planned:

### **Week 12 Primary Analysis**

The primary analysis of the trial will be performed once all randomised patients have completed the first 12 weeks of the trial, and a preliminary database lock will be done. Details of the analysis to be performed will be described in the TSAP which is planned to be finalized prior to achieving database lock for this primary analysis. Treatment will be unblinded at this time.

For further details regarding the maintenance and protection of the blind through the continuing trial subsequent to performance of the primary analysis, refer to [Section 4.1.5.1](#).

### **Final Trial Analysis**

The final analysis of the trial will be performed once all randomised patients have completed the trial. At this time, the treatment will be officially unblinded.

Adherence to the protocol (such as inclusion/exclusion criteria, times of measurement, compliance with intake of trial medication, treatment dispensing errors, prohibited concomitant medication, completeness and consistency of data) will be checked. Important protocol deviations (IPDs) will be identified in an initial version of the TSAP and will be updated no later than in the Report Planning Meeting and will be provided in the final Trial Statistical Analysis Plan (TSAP).

The handling of patients who received a wrong treatment will be described in the TSAP.

#### **7.3.1 Primary endpoint analyses**

##### **Primary analysis**

The analysis of the gene expression values will be based on the RSS and will be conducted for biopsy location inner orifice and curettage. The analyses will be done by 'actual treatment'.

All analyses will be performed using the raw read counts for gene expression. This gene expression analysis is conducted for biopsy.

The RNA expression analysis will initially include all genes and all determined read counts. This means, if no gene expression values have to be excluded due to technical or other reasons, there is one read count value per person, per gene and per time point.

To get interpretable results several pre-processing steps are needed to correct e.g. for different sequencing depth. The following steps are conducted:

- Lowly expressed genes are filtered:
  - Genes for which at least 5 samples display a  $\text{cpm} \geq 1$  are used in the subsequent analyses.
  - normalization factors to scale the samples based on the raw library sizes are calculated using the weighted trimmed mean of M-values (TMM) method using the default parameters of edgeR's `calcNormFactors` function ([R18-2554](#)).

After these pre-processing steps the  $\log_2$  counts per million along with associated weights for each observation are then calculated based on the normalized library sizes from the previous step using limma's `voom` function [[R15-5383](#)]. Correlations between paired measurements per patient are estimated by the `duplicateCorrelation` function. For each gene, a repeated measures linear regression model will be utilized with treatment (BI 655130 or Placebo), visit (baseline, week 4), treatment by visit interaction as fixed effect and patient as a blocking factor. Hereby the weights for each observation are taken into account (13). This will be implemented using the `lmFit` function of the limma package.

Estimates for the mean  $\log_2$  fold change ratio for BI 655130 vs. Placebo at Week 4 will be calculated as

$$\log_2 \text{FC}_{\text{BIvsPBO}} = (\log_2 \text{BI}_{\text{Week 4}} - \log_2 \text{BI}_{\text{BL}}) - (\log_2 \text{PBO}_{\text{Week 4}} - \log_2 \text{PBO}_{\text{BL}}),$$

where baseline is the measurement at Visit V1c.

Changes will be quantified by  $\log_2$  fold changes (FC) and associated FDR adjusted p-values. Genes will be considered deregulated if they fulfil the following criteria:

- FDR adjusted p-value  $\leq 0.05$
- $|\text{fold change}| \geq 1.5$  ( $|\log_2 \text{fold change}| \geq 0.58$ )
- genes can be annotated with Ensembl identifiers (version 84 or later)

The total number of deregulated genes at Week 4 will be reported.

[REDACTED]

[REDACTED]

[REDACTED]

### 7.3.2 Secondary endpoint analyses

The analysis of efficacy endpoints will be based on the FAS and will be done by 'planned treatment'.

The secondary efficacy endpoints regarding proportions of patients will be described descriptively. 95% confidence intervals for the rate difference will be provided, if feasible.

AEs will be tabulated by system organ class and preferred term after coding according to the current version of MedDRA. In the same way, summaries will be prepared for SAEs and for the frequency of AEs by intensity (according to RCTC).

Laboratory data will be compared to their reference ranges. Values outside the reference range will be flagged. Additionally, differences from baseline will be evaluated.

For vital signs, the differences from baseline will be evaluated.

Relevant ECG findings will be reported as AEs.

[REDACTED]

[REDACTED]

[REDACTED]

[REDACTED]

#### 7.4 INTERIM ANALYSES

The primary analysis of the efficacy and safety data collected up to week 12 will be performed once all randomised patients have completed the first 12 weeks of the treatment period (through visit 6). At that time point, a preliminary database lock will be done. Since the patients will be treated for another 12 weeks, the patients and the investigators (as well as the research staff at the trial site) must remain blinded. A logistics plan will be developed in order to describe the processes to be implemented for protecting the blinding (with regards to the patients and the investigators) and the integrity of the ongoing trial until the final database lock. Details of the analyses to be performed for the primary analysis, as well as for the final analysis after trial completion (through 36 weeks), will be described in the trial statistical analysis plan. Both the TSAP and the logistics plan will be finalized prior to the preliminary database lock for the primary analysis.

The primary analysis and final analysis may be performed as a single analysis (at the time of trial completion), if, prior to the time of the primary analysis, the trial team agrees that the expected time interval between the planned analyses is insufficient to justify the performance of separate analyses.

Further, a fully external DMC will be in place in order to ensure that patients are protected from potential harm, specific tasks are described in [Section 8.7](#).

#### 7.5 HANDLING OF MISSING DATA

With respect to safety evaluations, it is not planned to impute missing values.

No imputations for the primary endpoint and for any missing BM data are planned.

For disease specific [REDACTED] the following handling of data below or above the limit of quantification will be applied:

- BLQ data will be replaced by 0.5 times the LLOQ
- ALQ data will be replaced by ULOQ, if ULOQs are available. Otherwise, ALQ data will be excluded from the analysis.

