#### 5.4 ASSESSMENT OF BIOMARKER(S)

This section refers to exploratory biomarkers. Established biomarkers of efficacy and safety are described and discussed in [sections 5.1](#) and [5.2](#).

In the *Screening Cohort* biomarkers from various biopsies including inner fistula orifice, curettage at the fistula canal, outer fistula orifice, and rectal luminal biopsies will be analyzed (cf. [Flow Chart A](#)).

For the *Study Cohort* blood samples (serum), [REDACTED] will be collected at time points indicated in the [Flow Chart B](#) and [C](#) for the analysis of biomarkers.

All remaining samples will be destroyed no later than one year after end of the trial.

[REDACTED]

[REDACTED]

[REDACTED]

[REDACTED]

[REDACTED]

[Redacted text block]

[Redacted text block]

[Redacted text block]

[Redacted text block]

[Redacted text block]

[Redacted text block]

[Redacted text block]

[Redacted text block]

[Large redacted text block]

[REDACTED]

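### Values above the assay range are left out of the analysis when no upper limit is available; this informative removal can bias change from baseline in either direction

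*Protocol*

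**What the plan says.** Protocol 7.5 (Handling of missing data) sets the rule for results outside the assay range. For a type of disease-specific data whose name is blacked out, "the following handling of data below or above the limit of quantification will be applied":

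- Low end: "BLQ data will be replaced by 0.5 times the LLOQ".
- High end, limit known: "ALQ data will be replaced by ULOQ, if ULOQs are available".
- High end, limit not known: "Otherwise, ALQ data will be excluded from the analysis".

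The same section states: "No imputations for the primary endpoint and for any missing BM data are planned". So nothing puts an excluded value back into a summary. Protocol 7.3 adds "All individual data will be listed", so the values stay in the record and are lost only to the analysis.

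The readable SAP does not change the rule. SAP 6.6 refers to Protocol 7.5 for missing data. SAP 4 declares agreement with the protocol's methods and changes only the term for the rate difference. The SAP abbreviation list includes ALQ, BLQ, LLOQ and ULOQ, but no readable SAP section uses them in a rule. SAP 6.6.4, 6.6.5 and 6.6.7 are blacked out.

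**The concern.** A result flagged ALQ is not missing. Its exact value is unknown, but it is known to lie above everything the assay could quantify. Leaving it out makes inclusion depend on the outcome, and only at one end: low results are always kept, while high results are dropped whenever no limit is on file.

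In a change-from-baseline summary, an ALQ baseline removes the patient for that analyte. An ALQ follow-up value removes the patient for that analyte at that visit. If ALQ results are unevenly spread over visits or arms, the patients left no longer represent the arm. With about 10 patients per arm (Protocol synopsis), each one lost is about a tenth of an arm. Understanding the mode of action is a main objective (Protocol 2.1.1), so marker summaries would be read with interest even though nothing is tested in a confirmatory sense.

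**Working it through.** **No plan figure to reproduce.** Protocol 7.7 bases the sample size on feasibility. The documents give no ALQ rate, ULOQ, SD or expected marker effect, so the inputs below are assumptions, apart from the arm size of about 10.

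**Assumptions.** Values are normal on the log scale, with baseline mean 0 and SD 1. Changes are in baseline SDs. One limit U applies at both visits. ALQ at baseline is 5%, 10% or 20%; the correlation ρ between visits is 0.3, 0.5 or 0.7; follow-up SD is 1.0 or 1.3; the true change δ runs from +0.3 to −0.8.

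**Step 1: direction, in closed form.** Take 10% ALQ at baseline (U = 1.282), ρ = 0.5, equal SDs and δ = −0.30. Let λ(x) = φ(x)/Φ(x), where φ and Φ are the standard normal density and distribution function.

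- Only ALQ baselines excluded: apparent change = δ + (1 − ρ)·λ(U). Here λ(1.282) = 0.1755/0.900 = 0.195, so −0.30 + 0.5 × 0.195 = **−0.20**. The fall is understated.
- Only ALQ follow-up values excluded: apparent change = δ − (1 − ρ)·λ(U − δ). Here λ(1.582) = 0.1142/0.9431 = 0.121, so −0.30 − 0.5 × 0.121 = **−0.36**. The fall is overstated.

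**Step 2: rule applied at both visits** (simulation, 1,000,000 pairs per scenario, paired change; 10% ALQ at baseline, ρ = 0.5).

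| True change | Apparent, follow-up SD 1.0 | Apparent, follow-up SD 1.3 |
|---|---|---|
| 0 | 0.00 | −0.15 |
| −0.30 | −0.26 | −0.39 |
| −0.80 | −0.72 | −0.81 |

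Over the whole grid, a true −0.30 appears as −0.22 to −0.42, and a true −0.80 as −0.62 to −0.84.

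**Step 3: between-arm difference** (active δ = −0.80, placebo δ = 0; true difference −0.80).

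- Equal SDs: −0.72 − 0.00 = −0.72.
- Follow-up SD 1.3: −0.81 − (−0.15) = −0.66.
- Whole grid: −0.77 to −0.56, that is 0.77/0.80 = 96% down to 0.56/0.80 = 70% of the true difference. It shrank in every scenario.

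**Step 4: chance that an arm of 10 has at least one ALQ baseline**, 1 − (1 − q)^10.

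- q = 5%: 1 − 0.95^10 = 40%.
- q = 10%: 1 − 0.90^10 = 65%.
- q = 20%: 1 − 0.80^10 = 89%.

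These are rates of ALQ results. They say nothing about how often the ULOQ is also unavailable.

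**Step 5: what keeping the values would gain.** Capping at the ULOQ is not a fair comparator, because this branch applies only when no ULOQ exists. The usable fallback is the highest quantified value in the trial data. Simulated with 10 per arm, 10% ALQ at baseline and ρ = 0.5, against a true difference of −0.80:

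- Equal SDs: −0.75, against −0.72 under exclusion.
- Follow-up SD 1.3: about −0.71 (repeat runs lie between −0.70 and −0.71), against −0.66 under exclusion.

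The shortfalls under exclusion are 0.80 − 0.72 = 0.08 and 0.80 − 0.66 = 0.14. The fallback recovers about 0.03 and 0.05 of them, roughly a third.

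**The case against.** **The branch may be empty.** A laboratory usually flags a result as ALQ against some limit, and when that limit is on file the protocol already substitutes it. No readable section says that any assay lacks a ULOQ or how many ALQ results are expected. This stands, and it is the main reason the point is minor.

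**The endpoints that matter are out of reach.** The primary endpoint rests on sequencing counts ("All analyses will be performed using the raw read counts for gene expression"), with no assay ceiling mentioned. The secondary endpoints are clinical and MRI-based. Of its biomarkers, Protocol 5.4 says "This section refers to exploratory biomarkers". This stands on the readable text. SAP 3 lists CRP and faecal calprotectin among the week 12 analyses, but whether this rule covers them cannot be read.

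**The scope and the final rule are partly hidden.** That the data are biomarkers is an inference from a blacked-out noun, and the blacked-out SAP sections may refine the rule. Both stand as limits. However, SAP 4 declares no such change, and the protocol sentence is current text.

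**Medians are already planned.** SAP 7 includes them in the standard summaries. This does not help, because an excluded value does not enter the median either.

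A reader might also infer that the rule understates falls from baseline. The documents do not support this as a general statement: it needs ALQ results mainly at baseline, and nothing says where they will fall. When they fall at follow-up, or when follow-up values are more spread out, the rule can overstate a fall or create one.

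**Conclusion.** The point holds in limited form. Excluding ALQ values when no ULOQ is available removes the highest values selectively, while low values are always kept. Within an arm, change from baseline can be biased either way. With 10% ALQ at baseline, correlation 0.5 and follow-up SD 1.3, no true change appears as −0.15. The between-arm difference shrank throughout the grid, to between 70% and 96% of its true size. That pattern was found in the scenarios tried and is not a theorem. All sizes rest on the assumed log-normal values, ALQ rates, correlations and SDs; the documents do not allow the real size to be determined.

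Two further inferences go too far. The values are not deleted from the trial record, since individual data are listed. Nor does the rule put the trial's primary or secondary results at risk on the readable text.

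**What to change.** In Protocol 7.5, replace the sentence "Otherwise, ALQ data will be excluded from the analysis" with a rule that keeps these values, and carry it into the SAP if the blacked-out sections do not already do so:

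- Where no ULOQ is available, set an ALQ result to the highest quantified value of that analyte in the trial data, or treat it as right-censored.
- Summarise that analyte by medians or ranks, with ALQ results given the highest rank.
- Report the number of ALQ results per arm and visit.

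The cost is a few sentences and one count table; no new data are needed. There are drawbacks. A capped value still somewhat understates the true level, and the cap depends on the data. A patient who is ALQ at both visits gets a change of zero under the cap, although the true change is unknown; the counts make such cases visible. As Step 5 shows, the gain for means is modest.
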